3.6.4 Expedited Reporting

Reporting to the Data and Safety Monitoring Committee (DSMC)

If a death occurs during the treatment phase of the study or within 30 days after the last administration of the study drug(s) and it is determined to be related either to the study drug(s) or to a study procedure, the Investigator or his/her designee must notify the DSMC Chair (or qualified alternate) within 24 business hours of knowledge of the event. The contact may be by phone or e-mail.

Reporting to UCSF's Committee on Human Research (CHR)

The Investigator must report events meeting the CHR definition of “Unanticipated Problem” (UP) within 10 working days of his/her awareness of the event.

Guidance on Adverse Event Reporting to the CHR is available online at the [UCSF Human Research Protection Program](#) website.

Expedited Reporting to the Food and Drug Administration (FDA)

The Sponsor-Investigator is responsible for determining whether or not the suspected adverse reaction meets the criteria for expedited reporting in accordance with Federal Regulations (21 CFR §312.32).

The Investigator must report in an IND safety report any suspected adverse reaction that is both serious and unexpected. The Sponsor-Investigator needs to ensure that the event meets all three definitions:

- Suspected adverse reaction
- Serious
- Unexpected

If the adverse event does not meet all three of the definitions, it should not be submitted as an expedited IND safety report.

The timeframe for submitting an IND safety report to FDA is no later than **15 calendar days** after the Investigator determines that the suspected adverse reaction qualifies for reporting (21 CFR 312.32(c)(1)).

Any unexpected fatal or life-threatening suspected adverse reaction must be reported to FDA no later than **7 calendar days** after the Investigator's initial receipt of the information (21 CFR 312.32(c)(2)).

Any relevant additional information that pertains to a previously submitted IND safety report must be submitted to FDA as a Follow-up IND Safety Report without delay, as soon as the information is available (21 CFR 312.32(d)(2)).

The investigator (or designee) should prepare [Form FDA 3500A \(MedWatch\)](#) detailing the event, and contact the Institutional Trials Unit for assistance in the preparation of the IND Safety Report.

For additional information and guidance on IND Safety Reports, please refer to FDA's Guidance document [Safety Reporting Requirements for INDs](#).

Reporting to Genentech and Novartis

Genentech

Serious AE and AEs of Special Interest (regardless of causality) will be transmitted to Genentech within 24 hours of the Awareness Date. The completed MedWatch/case report should be faxed immediately upon completion to **Genentech Drug Safety** at:

[contact] OR [contact]

Additional Reporting Requirements to Genentech include the following:

- Any reports of pregnancy following the start of administration with the vemurafenib will be transmitted to Genentech within thirty (30) calendar days of the Awareness Date.
- All Non-serious Adverse Events originating from the Study will be forwarded in a quarterly report Genentech.
- Relevant follow-up information should be submitted to Genentech Drug Safety as soon as it becomes available.

Reconciliation

The Sponsor agrees to conduct reconciliation for the product. Genentech and the Sponsor will agree to the reconciliation periodicity and format, but agree at minimum to exchange monthly line listings of cases received by the other party. If discrepancies are identified, the Sponsor and Genentech will cooperate in resolving the discrepancies. The responsible individuals for each party shall handle the matter on a case-by-case basis until satisfactory resolution.

Novartis

All events must be reported by [contact]) to Novartis Pharmaceuticals DS&E Department within 24 hours of learning of its occurrence using an SAE Report form provided by Novartis. This includes serious, related, labeled (expected) and serious, related, unlabeled (unexpected) adverse experiences. All deaths during treatment or within 30 days following completion of active protocol therapy must be reported within 5 working days. The original copy of the SAE Report and the fax confirmation sheet must be kept within the Study File.

Relevant follow-up information should be submitted to Novartis Drug Safety as soon as it becomes available. Follow-up information is sent to the same person(s) to whom the original

SAE Report Form was sent, using a new SAE Report Form stating that this is a follow-up to the previously reported SAE and giving the date of the original report. Each re-occurrence, complication, or progression of the original event should be reported as a follow-up to that event regardless of when it occurs. The follow-up information should describe whether the event has resolved or continues, if and how it was treated, and whether the patient continued or withdrew from study participation.

If the SAE is not previously documented in the BKM120 or vemurafenib Investigators' Brochure or Package Insert (new occurrence) and is thought to be related to the study drugs, a Drug Safety and Epidemiology Department associate may urgently require further information from the investigator for Health Authority reporting. Novartis may need to issue an Investigator Notification (IN), to inform all investigators involved in any study with the same drug that this SAE has been reported. Suspected Unexpected Serious Adverse Reactions (SUSARs) will be collected and reported to the competent authorities and relevant ethics committees in accordance with Directive 2001/20/EC or as per national regulatory requirements in participating countries.

3.6.5 Oversight and monitoring

The UCSF Helen Diller Family Comprehensive Cancer Center (HDFCCC) Data Safety Monitoring Committee (DSMC) is responsible for monitoring data quality and patient safety for all UCSF-CCC institutional clinical studies. A summary of DSMC activities for this study includes:

- Review of subject data in each cohort
- Review of all serious adverse events
- Minimum of a yearly audit

3.6.5.1 Monitoring and reporting guidelines

Investigators will conduct continuous review of data and patient safety at monthly study group or site committee meetings where the results of each patient's treatment are discussed and the discussion is documented in the minutes. The discussion will include the number of patients, significant toxicities as described in the protocol, doses adjustments, and observed responses. All grade 3-5 AEs and SAEs will be entered in the HDFCCC OnCoreClinical Trial Management System (CTMS).

Review of Adverse Event Rates: If the study has an increase of unexpected or expected Adverse Event grade 3 or 4 above the rate reported in the Investigational Brochure or package insert, the increase rate of AEs will be reported to the DSMC at the time of Identification. The Chair and PI will discuss the finding and proceed with a written course of action. If at any time the Investigator stops enrollment or stops the study due to safety issues the DSMC Chair and Administrator must be notified within 24 business hours via e-mail. The DSMC must receive a formal letter within 10 business days and the CHR must be notified.

Data Safety Monitoring Committee Contacts:

DSMC Chair: [name]
 [contact]
 Email: [contact]
 Address: [name]
 UCSF Helen Diller Family
 Comprehensive Cancer Center
 [name]

DSMC Monitors - address
 [name]
 UCSF Helen Diller Family
 Comprehensive Cancer Center
 [name]

5.1 Study Design/Endpoints

This is a phase 1/2 clinical trial designed to determine the recommended phase 2 dose of PI3K inhibitor BKM120 in combination with BRAF inhibitor vemurafenib (phase 1) followed by a determination of 6 month progression-free survival rate (phase 2) in patients with BRAF mutant melanoma.

For Phase 1, Part A

This is a single-arm, open-label phase 1 clinical trial. The primary endpoint for phase I, part A is the RP2D of vemurafenib twice daily and BKM120 daily in BRAF mutant melanoma patients with no prior exposure to potent BRAF inhibitors and the primary safety endpoint is DLT. Phase 1 dose levels are described in *Table 5* and details regarding dose escalation and identifying the RP2D are given in section 3.3.2.1.

For Phase 1, Part B

The primary endpoint for phase 1, part B is the RP2D of vemurafenib twice daily in BRAF mutant melanoma patients with prior progression of disease on potent BRAF inhibitors and BKM120 daily and the primary safety endpoint is DLT.

For the Phase 2 portion

The primary endpoint of the Phase 2 portion is the progression-free survival rate at 6 months. Imaging assessments will be made by a radiologist, and final assessment using Response Evaluation Criteria in Solid Tumors (RECIST, version 1.1) will be made by the PI. Any documentation of a PR or CR in a target or non-target lesion must be confirmed by a repeat scan at least 4 weeks after the initial scan indicating the PR or CR. Disease response will be assessed at scheduled visits by diagnostic anatomic imaging, and clinical exam. All patients will be followed for 6 months and proportion of patients that are progression free at 6 months will be calculated.

Secondary Endpoints

Median PFS and OS defined by the Kaplan-Meier method. Tumor progression will be defined using RECIST version 1.1. Analysis of tolerability will be descriptive with reporting of all events by grade that are thought to be possibly, probably, and definitely attributable to study drug. Correlative assessments for PTEN expression, changes in pS6, and gene expression analysis are described in section 3.4.7 along with statistical analysis plans for these assessments.

5.2. Sample Size/Accrual Rate

This study will use the standard 3+3 dose escalation design to determine the RP2D of BKM120 in combination with vemurafenib (phase 1) followed by a single-stage binomial phase 2 design of 37 evaluable patients (any patient receiving at least 75% of prescribed cohort dose during the DLT period) to determine the PFS rate at 6 months.

For the Phase 1 portion

A Phase 1 dose escalation design using the standard 3+3 scheme will be followed and the sample size is not predetermined. We estimate the phase 1 portion of this trial will require a minimum of 2 patients from four predefined dose levels (see *Table 5*) to determine the phase 2 dose (MTD). The estimated maximum number of patients is 24. The final sample size of the study depends primarily on clinical considerations rather than on statistical considerations.

For the Phase 2 portion

The sample size for the phase 2 portion of this study is determined using single-stage binomial design for phase 2 studies. Preliminary data from trials of vemurafenibmonotherapy in advanced melanoma suggest a median PFS of approximately 6 months^{4,5,17}. The proposed design will be used to test the null hypothesis that the 6 month PFS rate of the study combination is 50% or less (which would not be clinically desirable) versus the alternative hypothesis that the true 6 month PFS rate is greater 70%, which would be considered clinically meaningful. The maximum total sample size will be 37 in Phase 2 including patients in the phase 1 portion of the study treated at the RP2D.

5.3 Analysis Plan

All patients who received at least 75% of prescribed cohort dose during the DLT period will be considered evaluable. Patients not evaluable will be replaced.

Phase 1 portion of the study

Safety and tolerability will also be assessed by clinical review of all relevant parameters including adverse experiences (AEs), laboratory tests, and physical exam. Adverse experiences will be summarized as counts and frequencies for each dose level. Other safety endpoints will be summarized as appropriate. These data are descriptive in nature and statistical analysis tools will not be required. The recommended phase 2 dose will be determined using safety data including DLTs and post-DLT toxicity, the dose-response relationship, and PK data.

Pharmacokinetic data will be acquired as described in section 3.4.6 and average values and standard deviations at each time point will be reported.

Phase 2 portion of the study

The PFS duration is defined as the time from the date of start of protocol therapy to the date of the first documented progression or death due to any cause. A patient who has not progressed or died by the date of the analysis cut-off or when the patient received any further anticancer therapy would have the PFS censored at the time of the last adequate tumor assessment before the first of the cut-off date or of the anticancer therapy date. All patients will be followed for 6 months and proportion of patients that are progression free at 6 months will be calculated. We assume that combination treatment will have at least 70% PFS rate versus the undesirable PFS of <50% at 6 months. The phase 2portion is designed based single stage binomial design with the type I alpha of 5% and the power of 80%. If ≥ 23 patients ultimately achieve 6 months PFS, then further investigation of the drug is warranted.

As secondary efficacy endpoints, the median PFSand OS will be estimated using exact binomial distribution; time to progression will be estimated using Kaplan-Meier methods. The 6-month PFS and 95% confidence intervals will be reported. ORR will be reported as frequencies and proportions with exact 95% confidence intervals from the Binomial distribution. The frequencies of individual toxicities thought to be probably, possible, or definitely related to study drug will be reported as well as the incidence of any grade 3, 4, and 5 toxicities regardless of attribution.

Correlative assessments for PTEN expression, changes in pS6, and gene expression analysis are described in section 3.4.7 along with statistical analysis plans.

6 Procedures and instructions

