3.1 Overall study design

Phase 1

Part A

The phase 1 portion of this trial is a 3+3 dose escalation study. In *Part A* of the phase 1 portion of the study, there will be a 7 day lead-in period (cycle 0) to allow for single dose pharmacokinetic analysis of BKM120 alone. Patients will receive continuous dosing of vemurafenib and BKM120 starting on cycle 1, day 1 (See *Figure 5*, Study design). Cycle 1 (28 days) will be defined as the DLT period.

Part B

In *Part B* of the phase 1 portion of the study, there will be no lead in period, but patients must discontinue BRAF therapy at least 2 weeks or 5 half-lives prior to starting combination therapy on trial (whichever is shorter). Patients with prior disease progression on a BRAF inhibitor will receive continuous dosing of vemurafenib and BKM120 starting on cycle 1, day 1 (See *Figure 5*, Study design). Cycle 1 (28 days) will be defined as the DLT period.

Part A & B

[figure not shown]
During the phase 1 portion of the study, vemurafenib and BKM120 doses will be escalated using a standard 3+3 dose escalation scheme with the goal of identifying the recommended phase 2 dose (RP2D). Phase 1 dose levels are described in *Table 5* and details regarding dose escalation and identifying the RP2D are given in section 3.3.2.1.

Phase 2

[figure not shown]
In the phase 2 portion of the study, patients will receive continuous dosing of vemurafenib and BKM120 starting on Cycle 1, Day 1 at RP2D.

Figure 5. Study design

[figure not shown]
Phase 1-Part A

Phase 1 – Part B

Phase 2

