3.3.4.3 Dose expansion and phase 2 dosing

After the RP2D is identified in Phase I, Part A, the RP2D cohort for BRAF inhibitor naïve patients will be expanded to a total of 37 patients for the phase 2 portion of the trial. Dose modifications in the phase 2 portion of the trial will be made as outlined in *Table 9*.

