3.3.5 Interruption or discontinuation of treatment

For patients who develop dose-limiting adverse events despite maximum supportive care after the DLT period in the phase 1 portion or at any time in the phase 2 portions of the study, dose adjustments are permitted. The criteria for dose adjustments for vemurafenib and BKM120 are described in *Table 8*. Since the study drugs have overlapping toxicities, the doses of both drugs will be reduced sequentially for all toxicities other than hyperglycemia, pneumonitis and anxiety, which are unique to BKM120. The dose levels for drug associated adverse events other than hyperglycemia, pneumonitis, and anxiety are outlined in *Table 9*. Reduction of the dose of BKM120 alone by increments of 20 mg per dose will be made for hyperglycemia, pneumonitis and anxiety with a maximum of 2 dose reductions permitted.

Table 8. Criteria for interruption and re-initiation of vemurafenib and BKM120 treatment

Recommended Dose Modifications for vemurafenib and BKM120

Worst toxicity (CTCAE Grade) **	Recommended Dose Modifications
No toxicity	Maintain dose level
HEMATOLOGICAL	
Neutropenia (ANC)	
Grade 1 (ANC < LLN - 1.5 x10 ⁹ /L)	Maintain dose levels
Grade 2 (ANC < 1.5 - 1.0 x 10 ⁹ /L)	
Grade 3 (ANC < 1.0 - 0.5 x 10 ⁹ /L)	Omit both drugs until resolved to ≤ Grade 1, and/or:
Grade 4 (ANC < 0.5 x 10 ⁹ /L)	
 • If resolved in ≤ 7 days, then maintain dose level • If resolved in > 7 days, then ↓vemurafenib/BKM120 1 dose level as outlined in Table 9
Febrile neutropenia (ANC < 1.0 x 10 ⁹ /L, fever ≥ 38.5°C)	Omit both drugs until resolved, then ↓vemurafenib/BKM120 1 dose level as outlined in Table 9
Thrombocytopenia	
Grade 1 (PLT < LLN - 75 x 10 ⁹ /L)	Maintain dose level
Grade 2 (PLT < 75 - 50 x 10 ⁹ /L)	
Grade 3 (PLT < 50-25 x 10 ⁹ /L)	Omit both drugs until resolved to ≤ Grade 1, and/or: 
 • If resolved in ≤ 7 days, then maintain dose level • If resolved in > 7 days, then ↓vemurafenib/BKM120 1 dose level as outlined in Table 9
Grade 4 (PLT < 25 x 10 ⁹ /L)	Omit both drugs until resolved to ≤ Grade 1, then ↓vemurafenib/BKM120 1 dose level as outlined in Table 9
HEPATIC	
Bilirubin (*for patients with Gilbert)	Will be fractionated if elevated

Table 8. Criteria for interruption and re-initiation of vemurafenib and BKM120 treatment**Recommended Dose Modifications for vemurafenib and BKM120**

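### The 75%-of-dose rule with replacement takes early deaths and early clinical progressions out of the PFS6 denominator, and the plan is inconsistent on what that denominator is

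*Combined protocol and SAP*

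**What the plan says.** Section 5.2 sizes phase 2 for PFS6 as "37 evaluable patients (any patient receiving at least 75% of prescribed cohort dose during the DLT period"). Section 5.3 repeats the rule above both its phase 1 and phase 2 headings: "All patients who received at least 75% of prescribed cohort dose during the DLT period will be considered evaluable. Patients not evaluable will be replaced". Neither section makes an exception for death, progression or toxicity.

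Section 5.3 defines PFS as "the time from the date of start of protocol therapy to the date of the first documented progression or death due to any cause". Section 5.1, and section 5.3 in the same words, also say: "All patients will be followed for 6 months and proportion of patients that are progression free at 6 months will be calculated".

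On numbers, section 5.2 says "The maximum total sample size will be 37 in Phase 2", counting phase 1 patients treated at the RP2D. Section 3.3.4.3 says the BRAF-inhibitor-naive RP2D cohort "will be expanded to a total of 37 patients for the phase 2 portion of the trial".

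The DLT period is defined in section 3.1 under phase 1 only: "Cycle 1 (28 days) will be defined as the DLT period". Section 3.3.5 keeps it apart from phase 2, allowing dose adjustments "after the DLT period in the phase 1 portion or at any time in the phase 2 portions of the study".

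**The concern.** The evaluable set is chosen by exposure after treatment has begun, and that exposure depends partly on outcome. Someone who dies on day 10 has a PFS event by the plan's own definition. The same patient cannot reach 75% of the cycle 1 dose, so is not evaluable and is replaced by a patient who lasted long enough to qualify. In a single-arm trial tested against a fixed 50%, removing certain failures moves the estimate in the drug's favour.

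PFS6 is the only stated basis for the phase 2 decision on further investigation. The plan does not explicitly define an all-treated PFS6 set beside the evaluable one. The sentence about all patients points to such a set, but it sits next to the explicit count of evaluable patients and nothing says which governs.

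**Working it through.** **Inputs.** Null 50%, alternative 70% and n = 37 (section 5.2). Alpha 5%, power 80% and success at 23 or more (section 5.3). DLT period 28 days (section 3.1). Six-month survival on vemurafenib 84% (section 1.2.2.1). First restaging at the end of week 8 (Table 11c, footnote 8). The share excluded, f, and the PFS6 rate among the excluded, q, are not in the documents; both are assumptions.

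**1. The plan's own figure.** An exact one-sided binomial test of 50% against 70% first meets alpha of at most 5% and power of at least 80% at n = 37, with a cut-off of 24:
- P(X ≥ 24 | 37, 0.5) = 0.0494
- P(X ≥ 24 | 37, 0.7) = 0.807

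So 37 reproduces. The printed cut-off of 23 gives 0.0939 and 0.887. That is a separate error, so the main figures here use 24.

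**2. Who leaves.** 0.75 × 28 = 21 days of full dosing, if the DLT period means cycle 1 in phase 2. Deaths and clinical progressions before about day 21 leave. Progressions found on scheduled scans, from week 8, stay in.

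**3. Effect on type I error.** If the true rate in all treated patients is 50%, the rate among evaluable patients is (0.5 − f·q)/(1 − f). Putting this into P(X ≥ 24 | 37):

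| f | q | Evaluable rate | Type I error |
|---|---|---|---|
| 0 | – | 50.00% | 4.94% |
| 2% | 0 | 51.02% | 6.35% |
| 5% | 0 | 52.63% | 9.17% |
| 10% | 0 | 55.56% | 16.51% |
| 2% | 40% | 50.20% | 5.20% |
| 5% | 40% | 50.53% | 5.63% |
| 10% | 40% | 51.11% | 6.49% |
| 10% | 60% | 48.89% | 3.71% |

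Rows with q = 0 are worst cases. At q = 50% there is no bias. Above 50% the error falls below its baseline.

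**4. Scale from the documents.** With a constant hazard (assumption), deaths by day 21 are 1 − 0.84^(21/182.6) = 2.0%, and 0.020 × 37 is about 0.7 patients.

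**5. What 37 means.** If 37 is the number evaluable, the mean number treated is 37/(1 − f) = 37.8, 38.9 or 41.1 for f = 2%, 5% or 10%. If 37 is the number treated, replacement would exceed the stated maximum. The text supports either reading.

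**The case against.** The strongest reply is that the effect is small. Scheduled scans start after the window, so a reader who infers that early progressions in general drop out goes too far: only deaths and clinical progressions before about day 21 do. The one scale that can be built from the documents is about 0.7 deaths in 37, and 2% excluded with all failing gives 6.3%. The 9.2% and 16.5% figures need exclusion rates the documents do not give. This stands, and it limits the severity.

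Second, the rule also removes patients whose dosing was interrupted for toxicity. Some of them may continue and reach six months progression-free, so the net bias over all exclusions need not be upward (3.7% in the last row above). This stands too. The upward direction is established only for early deaths and progressions.

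Third, the sentence about all patients could be the intended denominator. It does not override the explicit count of 37 evaluable patients, so this shows inconsistent text and does not remove the problem.

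Fourth, a reader might infer that replacement flatly contradicts the maximum of 37. The documents do not support that: section 5.2 opens with 37 evaluable patients, and its later maximum can be read in the same sense. What remains is an ambiguity.

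**Conclusion.** The defect holds as a matter of wording. Followed literally, sections 5.2 and 5.3 remove patients who are PFS6 failures by the plan's own definition and replace them, and the same sections describe the denominator in two ways. Confidence in this is high.

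Confidence in the size is low. In the worst case, type I error at the cut-off of 24 rises from 4.9% to 6.3%, 9.2% or 16.5% for 2%, 5% or 10% excluded. These rest on assumed exclusion rates, on every excluded patient failing, and on the DLT period meaning cycle 1 in phase 2, which the documents define only for phase 1. The documents do not show that the decision would be seriously distorted; they show that the plan permits an avoidable selection in its primary endpoint. It should be fixed, and the correction is cheap.

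**What to change.** In sections 5.2 and 5.3:

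- Define the primary PFS6 set as all patients in the phase 2 population who start combination therapy at the RP2D, up to 37, with no replacement for early death, progression or toxicity.
- Include phase 1 patients at that dose only if they belong to that population. Section 3.3.4.3 points to Part A, BRAF-inhibitor-naive patients, whereas exclusion criterion 1 in section 3.2.2 leaves the phase 2 population open; reconcile the two. Otherwise Part B patients, who had progressed on a BRAF inhibitor, could be pooled in.
- Count early deaths and progressions as failures.
- Keep the 75%-dose set as a sensitivity analysis, and say what the DLT period means for phase 2 patients.
- State that 37 means treated patients.

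The cost is wording and a reported PFS6 that may be slightly lower; n stays at 37. Power at a cut-off of 24 is 0.81 if the 70% target was meant for all treated patients. If it was meant for evaluable patients and 2% or 5% of those treated fail early, the all-treated rate is 0.70 × 0.98 = 0.686 or 0.70 × 0.95 = 0.665, and power is 0.75 or 0.66. The sponsor should say which was intended.
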